## SYNOPSIS

Protocol Title: Noninvasive Subharmonic Aided Pressure Estimation of Portal Hypertension

Trial Objectives: The primary objectives of this trial are:

- Evaluate the use of *in vivo* subharmonic aided pressure estimation (SHAPE) as a first qualitative screening modality for determining the presence of portal hypertension in patients undergoing a transjugular liver biopsy compared to catheter based pressure measurements (as the reference standard)
- Determine if SHAPE measurements can provide a quantitative, noninvasive measurement of hepatic venous pressure gradient (HVPG) to monitor disease progression or treatment response in patients identified with portal hypertension by comparing the results to repeat biopsies and/or clinical outcomes

Trial Design: This is an open-label, non-randomized trial that will be conducted at two clinical sites, Thomas Jefferson University (TJU) and the Hospital of the University of Pennsylvania (HUP). Enrolled patients undergoing trans-jugular liver biopsy with hepatic vein pressure gradient (HVPG) measurements will receive a continuous infusion of Sonazoid® (GE Healthcare, Oslo, Norway) co-infused with 0.9% NaCl solution over a 5-10 minute time period using the setup and infusion rates described in GE Healthcare (GEHC) Protocol Supplement provided in Appendix B. Ultrasound imaging will be performed using a Logiq 9 scanner with a 4C transducer (GE Healthcare, Milwaukee, WI) and the SHAPE algorithm will be used to measure pressure values in the hepatic and portal veins. Data will be stored on a PC and compared to pressure-catheter measurements. Subjects identified in the initial examination as having portal hypertension (by HVPG results) will be monitored by SHAPE for up to 18 months. These subjects typically have surveillance CT or MRI scans every 6 months to screen for liver cancer, and at those times a repeat SHAPE examination will be performed (ideally within 1 month of their clinically indicated imaging follow up appointment). In patients who undergo more frequent screening (generally 3 month intervals), SHAPE exams will be performed at 6 month intervals. Any repeat trans-jugular liver biopsies performed in this population will also trigger a repeat SHAPE study. Results of blood test evaluations (performed every 3 months in this population), medication, concomitant imaging study or procedure (including endoscopies) will be noted (all blood tests and imaging are clinically indicated only and are not required by this protocol). The end point for this part of the study will be any one new complication (e.g., liver cancer) or a marked worsening in any complication, liver

transplantation, death, or the end of this clinical trial (after 3 years). We expect these patients will be monitored three times during the course of this clinical trial. The time to reach the end point will be noted if a new complication or a marked worsening in any complication occurs.

**Trial Population:** This trial will consist of up to 300 adults (21 years of age or older) undergoing trans-jugular liver biopsy with HVPG measurement at TJU or at HUP.

**Trial Procedures:** Subjects eligible for trial enrollment will be identified by the co-investigators, [name] (at TJU) and [name] (at HUP) from their patient population of subjects scheduled for a trans-jugular liver biopsy. The research coordinators for this study will explain the study to the patients at the respective clinical sites. The patient will be given time to consider the risks and benefits of the study and ask questions about participation. The coordinator will review the consent form with the patient and then the patient will be given the form to review. The patient, coordinator, and a study investigator will all sign the consent form. The patient will be given a copy of the signed consent form for their records.

After consenting to participate in this study, a full demographic profile, known drug allergies or intolerances, and review of the subject's medical/surgical history will be recorded. Patients with known cardiac shunts will be excluded from the study. If the subject is a woman of childbearing potential, she will have a urine pregnancy test (the results of which will be made available to the subject prior to study initiation).

Whenever a subject undergoes a trans-jugular liver biopsy with transcatheter free and wedged hepatic venous pressure measurements as part of their standard clinical care and agrees to participate in the study, we will perform the corresponding SHAPE measurement within the 3 hours of post-recovery observation to ease transportation for patients and ensure that hydration status and other variables, which could potentially affect portal pressures, are equivalent. Administration of Sonazoid will be performed under

direct supervision of a medical doctor. Additionally, resuscitation equipment will be in immediate proximity to the patient during Sonazoid infusion. Three vials (6 ml) of Sonazoid microbubbles (16  $\mu$ l per vial when reconstituted) will be prepared for each subject by resuspending each vial in 2 ml of water for injection, supplied by GEHC, as described in the instructions provided by GEHC (Appendix B). Infusions will be performed as described in Appendix B. All materials and supplies used for the infusion procedure will be identical to those described in GE Healthcare's current Sonazoid IND. Briefly, anintravenous cannula will be placed in a vein in the subject's arm. A 0.9% NaCl solution will be started and used to fill up the connecting tubes before being connected to a 3-way stopcock. The stopcock will then be connected to the extension tubing leading to the cannula. All three vials of suspended Sonazoid will be drawn into a 10 ml syringe, placed in a syringe pump at the same level or below the patient, and connected directly to the stopcock. After the stopcock to the 0.9% NaCl solution has been opened, the saline solution will be infused at a rate of at least 2 ml/min. Then, Sonazoid will be co-infused at the target rate of 0.024  $\mu$ l/kg body weight/minute (suspension infusion rate of 0.18 ml/kg/hour), but the rate may be reduced if necessary to achieve optimal levels of contrast. This infusion rate was selected based on our group's previous experiences with Sonazoid infusion in human subjects in general [Halpern et al. 2002; Landmark et al. 2008] and in SHAPE portal hypertension subjects in particular [Eisenbrey et al. 2013]. This dosing scheme is designed to avoid (or limit) the number of cases that has to be discarded due to insignificant enhancement in the hepatic veins (as in our pilot study; Eisenbrey et al. 2013). The dosage is based off the GEHC provided, study specific resuspension and infusion instructions (Appendix B) and the total Sonazoid dose given over a maximum of 15 minutes (0.36  $\mu$ l/kg) will be well below the maximal tested dose which was still found safe in Phase I clinical trials (2.7  $\mu$ l of microbubbles/kg in PBI 0001 as detailed in the Sonazoid Investigator's Brochure). The duration of contrast agent infusion will range from 5 to 10 minutes.

After beginning the contrast infusion, a modified Logiq 9 scanner (GE Healthcare) with a broad bandwidth curvi-linear array (model 4C) will be used to obtain RF data (for SHAPE measurements) within the hepatic and portal veins. Both the experimental machine and software will be labeled as an

investigational device with a GRC provided label prior to beginning any clinical experiments (21 CFR 812.5). Once the infusion of Sonazoid has started, ultrasound imaging will be performed with the 4C curved linear array to guide SHAPE ROI placement into the portal vein (while also visualizing a hepatic vein). The SHAPE optimization algorithm will be activated ([Dave et al. 2013]) and the acoustic power will be adjusted to produce the maximum change in subharmonic amplitudes (i.e., maximizing the sensitivity of SHAPE). Then the ROI will be increased to visualize the hepatic and the portal veins, and the corresponding subharmonic data will be acquired at the optimal acoustic power setting in 5 s segments during the infusion of the Sonazoid suspension. Ultrasound imaging will be performed at a transmit frequency of 2.5 MHz and the subharmonic obtained at 1.25 MHz. All measurements will be repeated three times. The depths, sizes, and locations of the portal and hepatic veins will be determined by the sonographer and saved in a reference image.

The proposed agent for the study, Sonazoid (GE Healthcare,), is a sterile non-pyrogenic suspension of lipid stabilized perfluorobutane microbubbles for contrast-enhancement, with a median diameter between 2.4 and 3.5  $\mu\text{m}$  (Forsberg et al. 2008). Previous *in vitro* results have shown Sonazoid to be superior for SHAPE measurements relative to other ultrasound contrast agents (Halldorsdottir et al. 2011). The United States Food and Drug Administration (FDA) has yet to approve Sonazoid for human use in this country. Consequently, we intend to apply to the FDA for an investigator initiated IND (investigational new drug) to cover the use of Sonazoid in patients undergoing a trans-jugular liver biopsy. It should be pointed out that the safety of Sonazoid has already been established in numerous animal studies and in human studies for the evaluation of the liver and heart both in this country and in Europe (Landmark et al. 2008). Sonazoid has been approved for use in patients with liver lesions in Japan and has been marketed in that country since early 2007, and has been approved more recently in South Korea (Bouakaz et al. 2007; Jang et al. 2013). Finally, no adverse reactions attributable to contrast agent infusions were observed in our pilot study (Eisenbrey et al. 2013).

All examinations will be recorded. During the examination, the subharmonic pressure estimates will be

displayed on the Logiq 9 scanner, these estimates will be noted down and the data will be stored on a PC. Data will be compared to the transcatheter portal pressure measurements, which comprise the free and wedged hepatic venous pressure (FHVP and WHVP, respectively) and the hepatic vein pressure gradient (HVPG; measured as the difference between the WHVP and FHVP. Emergency services (e.g., a crash cart) will be available within the hospital in case of any acute adverse reactions. Subjects will be monitored for adverse reactions 2 hours post biopsy (roughly 1 hour post Sonazoid injection), again as a standard of care procedure. Patients will be monitored for a minimum of one hour post Sonazoid administration. During this time a trained CPR personnel and resuscitation equipment will be available. SHAPE data will later be compared to all clinical variables obtained from the patient to determine potential correlations to liver dysfunction.

**Statistical Methodology:** This project is a large clinical trial to further develop SHAPE and to employ this method to conduct a large scale human clinical trial to conclusively establish the accuracy of SHAPE for the assessment of portal hypertension. Our statistical analysis will address following major questions:

1. Can patients with HVPG of 10 mmHg or greater be identified using SHAPE? The fundamental hypothesis is that a sensitivity of 89% and a specificity of 81 % can be achieved by using SHAPE measurements to identify patients with HVPGs of 10 mmHg or greater.
2. Can portal vein pressures (in the form of HVPGs) in patients with liver disease be quantified accurately using SHAPE? The fundamental hypothesis is that a correlation coefficient of 0.82 can be achieved between *in vivo* SHAPE and HVPG measurements.
3. Can SHAPE accurately monitor disease progression or treatment response in patients identified with portal hypertension? The fundamental hypothesis is that correlation coefficients above 0.90 can be achieved between SHAPE and repeat HVPG results and that SHAPE will significantly differentiate responders from non-responders (using clinical outcomes as the reference standard).

The findings of SHAPE will be correlated to the invasive catheter based measurements of portal vein blood pressure (i.e., HVPG) using least squares, multiple linear regression analysis with robust standard errors. Comparisons of sensitivities, specificities and accuracies for diagnosing portal hypertension with SHAPE will be conducted with an unpaired Student's t-test (using HVPG measurements as the reference standard). Receiver operating characteristic (ROC) curves will be computed using a continuous scale

with HVPG cutoff levels of 10 and 12 mmHg. The optimal operating point (OOP) will be determined as the point closest to '0,1' on the ROC curve (representing 100% sensitivity and 100% specificity). All clinical variables (e.g., concomitant imaging results, presence of cancer or ascites, blood tests, fibrosis and MELD scores etc.) will also be compared to the SHAPE values. When both types of variables are ordinal or continuous, correlations will be calculated. When one type of variable is nominal and one continuous non-parametric rank order tests such as Mann-Whitney U-tests or Kruskal-Wallis tests will be performed [Rosner 1990]. All of the statistical analyses proposed for the human clinical trial will be repeated split by racial and ethnic groups to determine if clinically important race/ethnicity differences exist in the ability of SHAPE to diagnose portal hypertension.

All analyses and computations will be performed using NCSS/PASS 2008 and Stata 12.0 (Stata Corporation, College Station, TX), while the study database will be designed and implemented in Filemaker Pro 10.0 (Filemaker Inc, Santa Clara, CA). This database will contain all patient information (except names and other identifiers), including results of biopsies, HVPG and SHAPE measurements as well as the clinical variables.

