vials of suspended Sonazoid will be drawn into a 10 ml syringe, placed in a syringe pump at the same level or below the patient, and connected directly to the stopcock. After the stopcock has been opened, the NaCl solution will be infused at a rate of at least 2 ml/min, and Sonazoid will be infused at the desired rate of 0.024  $\mu$ l/kg body weight/minute (suspension infusion rate of 0.18 ml/kg/hour), but may be reduced if necessary to achieve optimal levels of contrast. This infusion rate was selected based on our group's previous experiences with Sonazoid infusion in human subjects in general [Halpern et al. 2002; Landmark et al. 2008] and in SHAPE portal hypertension subjects in particular [Eisenbrey et al. 2013]. This dosing scheme is designed to avoid (or limit) the number of cases that has to be discarded due to insignificant enhancement in the hepatic veins (as in our pilot study; Eisenbrey et al. 2013). This dosage is based on GEHC's previous experience of dosing Sonazoid by infusion. The maximum amount of microbubbles infused over 15 minutes (0.36  $\mu$ l/kg) is well below the maximal tested dose which was still found safe in Phase I clinical trials (2.7  $\mu$ l of microbubbles/kg in PBI 0001 as detailed in the Sonazoid Investigator's Brochure).

Sonazoid will be stored in a secure cabinet, with only the study investigators and research personnel having access. New vials must be prepared for each subject's contrast administration. Unused drug and empty vials will be properly disposed of after reconciling in the log of study drug.

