### 7.2.3 Sample Size Calculation

As the most clinically important aim, the sample size analysis is based on specific aim 1 where each patient represents an independent entity. Based on our pilot study, the sensitivity and specificity of

SHAPE for the diagnosis of portal hypertension (i.e., HVPG > 10 mmHg) is 89% and 88%, respectively [Eisenbrey et al. 2013]. However, the confidence intervals achieved in the pilot study were (due to the limited sample size) very wide (worst case scenario: 52–100%). Hence, a power analysis was performed using NCSS/PASS 2008 (NCSS, East Kaysville, UT) to estimate the number of cases required to produce clinically acceptable 95% two-sided confidence intervals (for one correlation) [Newcombe 1998]. Table 2 below illustrates sample size calculations for the number of independent observations needed in the study population based upon 95% two-sided confidence intervals ranging from 0.06 to 0.10 for one correlation. A sample size between 259 and 278 subjects will provide 95% confidence intervals from 0.84 to 0.92 (i.e., a width of 0.08). A similar analysis was conducted based on the correlation between SHAPE and HVPG of 0.82 obtained in our pilot study [Eisenbrey et al. 2012a]. In that case to demonstrate that SHAPE can accurately measure HVPG values with a correlation coefficient of 0.82 requires between 264 and 343 patients (for confidence interval widths of 0.08 and 0.07, respectively). Hence, we selected a sample size for this study of 300 subjects.

Table 2: Sample size calculations for different 95% confidence intervals in the human clinical trial.

Target width	Proportion (R)	Lower limit	Upper limit	Sample size (N)
0.06	0.88	0.848	0.908	483
0.06	0.89	0.857	0.917	450
0.07	0.88	0.842	0.912	359
0.07	0.89	0.851	0.921	335
0.08	0.88	0.836	0.916	278
0.08	0.89	0.845	0.925	259
0.09	0.88	0.830	0.920	222
0.09	0.89	0.839	0.929	207
0.10	0.88	0.824	0.923	181
0.10	0.89	0.833	0.933	170

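### The plan foresees discarding scans with inadequate hepatic-vein enhancement and names no other handling, so accuracy for a screening test would describe technically successful scans only

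*Combined protocol and SAP*

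**What the plan says.** The Synopsis (Trial Procedures) justifies the infusion rate partly by the wish to "avoid (or limit) the number of cases that has to be discarded due to insignificant enhancement in the hepatic veins", and points to the pilot as the place where such cases arose. Section 5 repeats it: "This dosing scheme is designed to avoid (or limit) the number of cases that has to be discarded". Section 6.2 has the same sentence.

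The analyses are in sections 6.4 and 7.2.2: least-squares regression of SHAPE against HVPG, and ROC curves on the continuous SHAPE scale at HVPG cut-offs of 10 and 12 mmHg, with the operating point read from the curve. Neither section defines an analysis set, a criterion for an adequate scan, or the treatment of a patient without a usable SHAPE value. Section 6.7.1 counts a subject as complete after an infusion and a full imaging study; enhancement is not mentioned.

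Section 7.2.3 sizes the trial on pilot accuracy: "SHAPE for the diagnosis of portal hypertension (i.e., HVPG > 10 mmHg) is 89% and 88%, respectively". It then states: "A sample size between 259 and 278 subjects will provide 95% confidence intervals from 0.84 to 0.92". For the correlation of 0.82 it "requires between 264 and 343 patients (for confidence interval widths of 0.08 and 0.07, respectively". It concludes: "Hence, we selected a sample size for this study of 300 subjects". Section 4 and the recruitment paragraph of 7.2.3 treat 300 as the number enrolled, and section 4 makes it a ceiling.

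**The concern.** The SHAPE measure that is compared with HVPG is a gradient between the portal and hepatic veins (section 1). Without adequate hepatic-vein signal there is no usable gradient, so the patient has no value to enter in the regression or the ROC curve. The only handling the documents name for such a case is discarding it, and the statistical sections do not replace it with another.

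Sensitivity and specificity would then be conditional on a successful scan. Both the first objective and the first hypothesis concern a screening use, namely whether SHAPE can identify patients with HVPG of 10 mmHg or greater. A patient whose scan gives no reading has not been identified either way, and a reader of the results would need to know how often that happens.

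The decision to discard is also unprotected. The scan follows the catheter measurement, within the post-biopsy observation period. Section 5.3 says only that the trial drug needs no blinding. Nothing states who judges enhancement, by what standard, or whether that person knows the HVPG.

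**Working it through.** **Inputs.** Hypothesised sensitivity 0.89 and specificity 0.81 (Synopsis; section 7.2.1). Pilot values 0.89 and 0.88, required sizes 259, 278, 264 and 343, and the chosen 300 (section 7.2.3). The failure rate f is not in the documents, so 5% to 30% is assumed.

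**Step 1: reproduce the plan's sizes.** Table 2 is introduced as giving "95% two-sided confidence intervals ranging from 0.06 to 0.10 for one correlation", but its sizes are those of an exact (Clopper-Pearson) interval for one proportion. With x = np, the limits are the 0.025 quantile of Beta(x, n − x + 1) and the 0.975 quantile of Beta(x + 1, n − x). Taking the smallest n whose width is within target returns all ten rows. For p = 0.88, n = 278, the interval is 0.8359 to 0.9158. For p = 0.89, n = 259, it is 0.8454 to 0.9254.

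The 264 and 343 follow from Fisher's z, tanh(atanh(r) ± 1.96/√(n − 3)). For r = 0.82, n = 264: atanh(0.82) = 1.1568 and 1.96/√261 = 0.1213, giving 0.776 to 0.856, width 0.080.

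The 300 comes from no formula. It is a choice above 278 and between 264 and 343.

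**Step 2: loss that 300 can absorb at width 0.08.**

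- Against 278 (p = 0.88): (300 − 278)/300 = 22/300 = 7.3%
- Against 264 (r = 0.82): (300 − 264)/300 = 36/300 = 12.0%
- Against 259 (p = 0.89): (300 − 259)/300 = 41/300 = 13.7%

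Against 343 (r = 0.82, width 0.07), 300 is short even with no loss.

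**Step 3: interval width with 300 enrolled and 300(1 − f) evaluable.**

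| f | Evaluable | p = 0.88 | p = 0.89 | r = 0.82 |
|---|---|---|---|---|
| 0% | 300 | 0.077 | 0.074 | 0.075 |
| 5% | 285 | 0.079 | 0.076 | 0.077 |
| 10% | 270 | 0.081 | 0.078 | 0.079 |
| 20% | 240 | 0.086 | 0.083 | 0.084 |
| 30% | 210 | 0.093 | 0.089 | 0.090 |

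Even at 30% loss, every width stays below 0.10, the widest target in Table 2.

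**Step 4: accuracy over all patients, worst case.** With f equal in patients with and without disease, and every failed scan counted as wrong, accuracy over all patients = accuracy in successes × (1 − f).

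| f | Sensitivity, 0.89(1 − f) | Specificity, 0.81(1 − f) |
|---|---|---|
| 5% | 84.6% | 77.0% |
| 10% | 80.1% | 72.9% |
| 20% | 71.2% | 64.8% |

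Starting from the pilot specificity of 0.88 instead, the last column would be 83.6%, 79.2% and 70.4%.

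**Step 5: dependence on the convention, at f = 10%.** If a failed scan is treated as test-positive, sensitivity is 0.801 + 0.10 = 90.1% and specificity stays at 72.9%. If it is treated as test-negative, sensitivity is 80.1% and specificity is 0.729 + 0.10 = 82.9%. No single convention gives both favourable values.

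**The case against.** The strongest reply is that the sentence on discarded cases justifies an infusion rate and is not an analysis rule. It states an aim to avoid or limit losses and predicts none. All examinations are to be recorded, measurements are taken three times, and the completion rule in section 6.7.1 would not exclude a poorly enhanced scan. This stands as far as it goes. A reader might infer that discards are expected, or that an evaluable-only analysis has been prescribed; the documents support neither. They do allow that the number may not be zero, they name discarding and nothing else, and they plan analyses that a patient without a value cannot enter.

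A reader might also infer that the sample size leaves no room for loss. None is labelled, but step 2 shows an unlabelled margin, and step 3 shows that crossing 278 changes little. The 278 is itself a soft benchmark. It uses total N, whereas sensitivity rests only on patients with HVPG of 10 mmHg or greater. That is a separate matter and larger for precision: at an assumed prevalence of 30% to 50%, the exact width for 0.89 is already 0.14 to 0.11 with no loss.

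A third tempting inference is that failures cluster in advanced disease and so bias the estimates selectively. Nothing in the documents says that enhancement varies with disease severity, so this is not claimed. Reporting the failure rate by HVPG group would settle it.

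Finally, counting failures as wrong is one convention among several, as step 5 shows, and it cannot be applied to a correlation or a continuous ROC curve. Both points stand and shape the fix.

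**Conclusion.** The point holds as a gap in what the accuracy estimates represent. Discarding is foreseen, no other handling is given, and the planned analyses need a SHAPE value, so the reported sensitivity and specificity would describe usable scans only. This is an inference from the named handling together with the silence of sections 6.4 and 7.2.2, not from a written exclusion rule.

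The size cannot be fixed from the documents, because neither the pilot's loss among its 45 patients nor an expected loss is given. The step 4 figures (sensitivity down to 80.1% at 10% failure and 71.2% at 20%) are a worst-case illustration. They rest on assumed rates, equal failure in both disease groups, and failures scored as errors.

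The effect on precision is minor: at p = 0.88 the exact width moves from 0.077 to 0.081 at 10% loss. The change is worth making before the data are analysed, but the point does not undermine the choice of 300.

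**What to change.** In sections 6.4 and 7.2.2:

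- Define inadequate enhancement in advance, and state who judges it without knowledge of the HVPG.
- Report the non-evaluable rate overall and separately for HVPG below 10 mmHg and for 10 mmHg or greater.
- Report sensitivity and specificity at the operating point twice: in evaluable scans, and in all infused patients with an HVPG, with non-evaluable scans counted as incorrect and the result labelled a worst case.
- Label the correlation and the ROC curve as evaluable-only, since a failed scan has no value to contribute.

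In section 7.2.3, state that the 0.08 width needs 278 evaluable patients (p = 0.88) or 264 (r = 0.82), so that the loss 300 can absorb is explicit.

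The cost is some added wording and one more table. The downside is an all-patients accuracy figure that is less favourable than the evaluable-only one. Enrolment need not change on this ground.

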In patients with chronic liver disease, transcatheter portal pressure measurement represents the “gold standard”, albeit indirect, for assessment of portal hypertension. The wedge hepatic venous pressure (WHVP) reflects values of portal venous pressure in cirrhosis (Sanyal et al. 2008). Another useful parameter is the gradient between the portal vein and the hepatic vein pressure, the hepatic vein pressure gradient (HVPG). The value of HVPG in assessing and monitoring several of the complications of portal hypertension is well established (D'Amico et al. 2006; Sanyal et al. 2008). It has also been found that an HVPG above 10 mmHg predicts the presence of varices, while an HVPG of 12 mmHg or more is required for varices to bleed (Garcia-Tsao 1985).

Variceal hemorrhage represents one of the most dramatic and immediately life threatening complications of portal hypertension and while the mortality rate has declined over the last decade it still ranges from 15 to 20% (Sanyal et al. 2008). Clinical management depends upon preventing an initial bleed when varices are present, intervening to stop active bleeding, and providing measures to prevent repeat bleeding. A sustained reduction in the HVPG to below 12 mmHg is the best predictor of successful reduction in the risk of bleeding with non-selective  $\beta$ -blockers. Likewise, a reduction in the risk of re-bleeding from varices is associated with a reduction in the HVPG of more than 20% from baseline or to less than 12 mmHg. Finally, the HVPG has been evaluated as a prognostic marker for disease progression, survival and mortality (Kalambokis et al. 2007). Most studies found that the HVPG, when added to other measures such as the Child Pugh or MELD scores, increased the ability to predict survival.

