## 2. TRIAL OBJECTIVES

Trial Objectives: The primary objectives of this trial are:

- Evaluate the use of *in vivo* subharmonic aided pressure estimation (SHAPE) as a first qualitative screening modality for determining the presence of portal hypertension in patients undergoing a transjugular liver biopsy compared to catheter based pressure measurements (as the reference standard)
- Determine if SHAPE measurements can provide a quantitative, noninvasive measurement of hepatic venous pressure gradient (HVPG) to monitor disease progression or treatment response in patients identified with portal hypertension by comparing the results to repeat biopsies and/or clinical outcomes.

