### 7.2 Statistical Analyses

#### 7.2.1 Hypotheses

$H_1$ : Can patients with HVPG of 10 mmHg or greater be identified using SHAPE? The fundamental hypothesis is that a sensitivity of 89% and a specificity of 81 % can be achieved by using SHAPE measurements to identify patients with HVPGs of 10 mmHg or greater.

H2: A correlation coefficient of 0.82 will be achieved between in vivo SHAPE and HVPG measurements.

H3: A correlation coefficients above 0.90 will be achieved between SHAPE and repeat HVPG results.

H4: SHAPE will significantly differentiate responders from non-responders using clinical outcomes as the reference standard.

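### H3 asks for r above 0.90 between SHAPE and repeat HVPG, but no planned analysis tests whether SHAPE changes when a patient's HVPG changes

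*Combined protocol and SAP*

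**What the plan says.** Section 2, like the Synopsis, makes it a primary objective to obtain a noninvasive figure for HVPG "to monitor disease progression or treatment response in patients identified with portal hypertension", judged against repeat biopsies, clinical outcomes or both. Question 3 of the Synopsis (Statistical Methodology) asks: "Can SHAPE accurately monitor disease progression or treatment response in patients identified with portal hypertension"? The hypothesis attached to it has two limbs: that "correlation coefficients above 0.90 can be achieved between SHAPE and repeat HVPG results", and that SHAPE separates responders from non-responders. Section 7.2.1 lists the limbs separately, as H3 ("A correlation coefficients above 0.90 will be achieved between SHAPE and repeat HVPG results") and H4 ("SHAPE will significantly differentiate responders from non-responders using clinical outcomes as the reference standard").

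Neither place says which SHAPE value is paired with the repeat HVPG, or whether levels or changes are meant. H3 has no null value, confidence limit or number of pairs.

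Section 7.2.2 plans multiple regression of SHAPE against HVPG with robust errors, ROC curves at HVPG 10 and 12 mmHg, and correlations or rank tests against clinical variables. It contains no change score, no adjustment for baseline and no within-patient model.

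Section 1.1 links a lower re-bleeding risk to "a reduction in the HVPG of more than 20% from baseline or to less than 12 mmHg". No hypothesis or analysis takes up the reduction from baseline.

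Section 7.2.3 bases the sample size on aim 1 and adds a calculation for "the correlation between SHAPE and HVPG of 0.82 obtained in our pilot study". It gives none for H3. Under Section 3, a repeat HVPG exists only if a repeat biopsy happens to be done during up to 18 months of follow-up.

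**The concern.** Patients differ from one another in HVPG, and much of that difference may persist between visits. A correlation of levels across patients reflects these standing differences as well as any change since baseline, and it cannot separate the two. Monitoring depends on the second part only: when a patient's HVPG rises or falls, does that patient's SHAPE value move with it?

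At stake is one of the two primary objectives. As written, it could be declared met or not met on a statistic that does not address it.

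**Working it through.** **Inputs.** From the documents: H3 bar 0.90; same-visit SHAPE–HVPG correlation r1 = 0.82; N of 264 and 343 for that correlation (Section 7.2.3). Assumed, because the documents do not give them: the correlation rho between a patient's first and repeat HVPG, the SDs of HVPG and of its change, and the number n of repeat pairs.

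**1. The plan's own figure.** The 95% interval is tanh(atanh(0.82) ± 1.96/√(N − 3)), with atanh(0.82) = 1.157.
- N = 264: 1.96/√261 = 0.121, interval 0.776 to 0.856, width 0.080.
- N = 343: 1.96/√340 = 0.106, interval 0.782 to 0.852, width 0.070.

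Both match. They concern the cross-sectional correlation, not H3.

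**2. A SHAPE that is blind to change.** Suppose SHAPE at the repeat visit carries only the baseline HVPG plus independent error. The expected level correlation at the repeat visit is then r1 × rho, and the correlation between SHAPE change and HVPG change is zero.

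| r1 | rho = 0.90 | rho = 0.95 | rho = 0.98 | rho = 1.00 | rho needed for 0.90 |
|---|---|---|---|---|---|
| 0.82 | 0.74 | 0.78 | 0.80 | 0.82 | 1.10 (impossible) |
| 0.92 | 0.83 | 0.87 | 0.90 | 0.92 | 0.978 |
| 0.95 | 0.86 | 0.90 | 0.93 | 0.95 | 0.947 |
| 0.98 | 0.88 | 0.93 | 0.96 | 0.98 | 0.918 |

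In a second model SHAPE follows only the stable part of each patient's HVPG. The repeat-visit level correlation then equals r1, again with zero correlation of changes. Simulation of 2,000,000 patients agreed with both models: for r1 = 0.82 and rho = 0.90 the level correlations were 0.74 and 0.82, and the change correlations were 0.00.

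A high level correlation and no tracking of change can therefore coexist. To exceed 0.90 in expectation, however, the same-visit correlation must itself exceed 0.90.

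**3. The limiting case.** Take a marker frozen at the patient's baseline HVPG and measured without error (r1 = 1.0), with change independent of baseline. Its correlation with repeat HVPG is SD_b/√(SD_b² + SD_change²).
- SD_b 5, SD_change 2 mmHg: 5/√29 = 0.93.
- SD_b 5, SD_change 2.4: 5/√30.76 = 0.90.
- SD_b 5, SD_change 3: 5/√34 = 0.86.
- SD_b 3, SD_change 2: 3/√13 = 0.83.

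At the documents' r1 the first two become 0.82 × 0.928 = 0.76 and 0.82 × 0.902 = 0.74.

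**4. Passing by chance.** H3 has no confidence limit, so a point estimate above 0.90 may be taken as success. Simulated probabilities (100,000 samples each):

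| True level r | n = 5 | n = 10 | n = 20 | n = 30 | n = 50 |
|---|---|---|---|---|---|
| 0.82 | 39% | 23% | 11% | 6% | 2% |
| 0.74 | 26% | 10% | 2% | 0.5% | about 0 |

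**5. The opposite error.** Let SHAPE equal HVPG plus an offset fixed for each patient, independent of HVPG, with SD k times the HVPG SD. The level correlation is 1/√(1 + k²). Setting this to 0.82 gives k = √(1/0.82² − 1) = √0.487 = 0.70. The offset cancels in the difference between visits, so the change correlation is 1.0. A perfect tracker of change then has an expected level correlation of 0.82 and misses H3.

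**The case against.** The strongest reply is that H3 is demanding. A reader might infer from the frozen-marker figures of 0.93 and 0.90 that a measure with no ability to detect change would pass H3 and be reported as able to monitor disease. The documents do not support that. Those figures need an error-free marker and favourable SDs; with the plan's 0.82, the bar is out of reach in expectation (steps 2 and 3). Nor does H3 merely repeat H2: it sets a higher bar, in a selected subset, at a later time. This part of the reply stands.

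Second, H3 is not the only monitoring test, since the Synopsis joins it to responder discrimination. That is true, but H4 does not close the gap. Its reference is clinical outcome, responder is undefined, and nothing in it requires change in SHAPE to follow change in HVPG. Section 1.1 describes HVPG as a prognostic marker, so a SHAPE value that reflects baseline severity alone might also separate outcome groups.

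Third, levels matter to monitoring: the Section 1.1 criterion includes reaching less than 12 mmHg, and an ROC curve at 12 mmHg is planned. This stands, and it is a reason to keep the level analysis. It does not supply the part that concerns reduction from baseline.

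Fourth, the text never states that H3 concerns levels. That is so. Levels is the natural reading, and if change was meant, the wording still has to say so.

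**Conclusion.** The concern holds in this form: H3, most naturally read as a correlation of levels, does not test whether SHAPE tracks change within a patient, and neither H4 nor Section 7.2.2 does. An r above 0.90 would not by itself support the monitoring objective, and an r below 0.90 would not refute it.

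The fixed-offset case shows the second half with the plan's own correlation: change correlation 1.0, level correlation 0.82. The first half should not be stretched into a claim that a change-blind SHAPE would routinely pass. With r1 = 0.82 its expected level correlation is at most 0.82 in both models, and a pass would be chance in a small repeat subset: 10% to 23% at 10 pairs and 2% to 11% at 20, for true correlations of 0.74 to 0.82.

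These sizes rest on assumed values of rho and n and on normally distributed data. The absence of any change analysis rests on the text alone.

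**What to change.** In Synopsis question 3 and Sections 7.2.1 and 7.2.2:

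- Make the H3 monitoring analysis, in patients with paired baseline and repeat HVPG, the regression (or correlation) of HVPG change, repeat minus baseline, on change in the SHAPE gradient, with a 95% CI. State which repeat is used if a patient has more than one.
- Report descriptively how well SHAPE classifies the whole Section 1.1 criterion, both the reduction of more than 20% and the fall to less than 12 mmHg. State how patients already below 12 mmHg at baseline are counted.
- Keep the level correlation at the repeat visit as supportive, and say which SHAPE value is paired with which HVPG.
- Report the number of pairs beside every estimate.

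The cost is wording: the plan already provides for a SHAPE examination at baseline and at any repeat biopsy. The drawback is precision. The change correlation is likely to be lower than the level correlation and may rest on few pairs. As an illustration, an observed correlation of 0.82 in 20 pairs has a 95% interval of tanh(1.157 ± 1.96/√17), or 0.59 to 0.93. If few repeat biopsies are done, the report should say that the monitoring question was answered only imprecisely.
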